#### 6.8 Valve Explants

Every effort should be made to return the explanted valve(s), at autopsy or explantation to Edwards. The explanted valve should be placed in a container with a suitable histological fixative such as 10% formalin or 2% glutaraldehyde immediately after excision and returned to Edwards. Refrigeration is not necessary under these circumstances. Contact Edwards Clinical Research for additional instructions.

Any pertinent information, e.g. operative notes, autopsy report etc should be sent to Edwards. All supporting data should be de-identified at the site to protect the privacy of the study subject.

This document and the information contained herein is considered Proprietary and Confidential and may not be reproduced, used or disclosed without written permission from Edwards Lifesciences LLC.

After the study valve is explanted, the subject will be followed for either an additional 30 days to monitor for any new adverse events or until all study device related serious adverse events are resolved. After that point the subject will be discontinued from the study. No further evaluations and/or case report forms are needed after study exit. Data from these subjects will be included in analysis

#### 6.9 Deaths/Autopsy Reports

All deaths that occur during study participation and deaths that occur 30 days post-study valve explantation shall be reported to the Edwards Clinical Affairs Department. The Investigator shall provide a written summary of the subject death including the cause of death and relationship of the death to the study valve or procedure. Copies of an autopsy report and/or death certificate shall be submitted to Edwards as permitted by local law. Death notifications shall be de-identified in order to protect the privacy of the subject.

#### 6.10 Subject Withdrawal

Although all subjects are informed of their right to withdraw from the clinical study at any time, it is anticipated that such withdrawals will be infrequent. All measures should be taken by the Investigator and their staff to encourage subjects to return for required follow-up visits. The clinical study objective may be jeopardized if large numbers of subjects are lost to follow-up.

All subjects are expected to continue in the study until Edwards notifies the Investigator, in writing that further follow-up is no longer required, except in the event of death or upon the subject's written request for early withdrawal from the clinical study. A copy of any request for subject withdrawal shall should sent to Edwards via the study monitor and a Subject Withdrawal case report form completed.

This document and the information contained herein is considered Proprietary and Confidential and may not be reproduced, used or disclosed without written permission from Edwards Lifesciences LLC.

Time Period						
Data Collection	Pre- Operative	Operative	Early Post- Operative /Hospital Discharge	Late Postoperative (3-6 Months)	1 Year (11-13 months) Annually	Unscheduled Visit
Informed Consent	X					
Study Eligibility	X					
Patient Status	x		х	x	X	
Physical Assessment	X		х	x	Х	
Electrocardiogram	X		x		Х	
Blood Studies	X			x	Х	
Pregnancy Test	X					
Medication Use	X		Х	x	Х	
Coagulation Profile	X		Х	x	Х	
Echocardiography	X		Х	X 	X 	X 
Quality of Life Survey (EQ-5D)	X 			X 		
Implant Procedure		x				
Concomitant Procedures		x				
Adverse Events		X	х	x	Х	x

#### Table 10. Study Schedule

 QOL surveys are required pre-operatively and at the 3-6 month visit.

 Echocardiograms are required at 6 months, 1 year, 2, 4, 6 and 8 year follow- up visits.

 If blood studies or echocardiograms performed at unscheduled visits, they should be recorded on the appropriate CRF, Echo data should be submitted to the Core Lab for evaluation.

# 6.11 Core Laboratory

Independent Core Laboratory evaluation of all Doppler echocardiograms will be performed using common protocols and CRFs. The purpose of a Core Laboratory is to ensure unbiased, timely and consistent analysis of this diagnostic data. A Core Lab is responsible for evaluating changes in study subject status over the course of the study based on serial studies in the same study subject. Core Lab personnel shall be qualified

This document and the information contained herein is considered Proprietary and Confidential and may not be reproduced, used or disclosed without written permission from Edwards Lifesciences LLC.

by training and experience in Doppler echocardiography data analysis. Edwards will ensure that Core Lab personnel are familiar with the study valve. Edwards or its designee will monitor Core Labs periodically to ensure adherence to data review schedules. Clinical Affairs will also perform audits of Core Labs at least once per year to ensure compliance with applicable study requirements

#### Doppler Echocardiograms

Echocardiographic studies shall be performed per the Core Lab Protocol found in Appendix 3. Sites shall send properly labeled compact discs or electronic copies of echocardiograms directly from the Study Sites to the Core Lab. The Core Laboratory will review the echocardiograms upon receipt and notify the Edwards promptly if the exam is of insufficient quality for analysis. Edwards will contact the site and request additional echocardiograms for analysis.

#### 7.0 ADVERSE EVENTS

An adverse event has been defined as any side effect, complication or medical consequence that has adverse health implications for the study subject receiving the study product/ treatment. Adverse events may be considered anticipated or unanticipated and shall be classified per the applicable definitions for the countries in which the study is being conducted.

The Investigator at each participating center is responsible for reporting adverse events (complications) to the Edwards or its designee regardless of whether they are considered to be related to the study procedure or study device. The Investigator shall complete the appropriate adverse event case report forms (See CRFs in Attachment 5) at each study visit, indicating the relationship of the event to the study device or procedure. The adverse event CRF for a given visit must report all adverse events that have occurred since the last documented visit. For example, all adverse events occurring after the Discharge visit, but prior to the 3-6 months postoperative visit should be reported on the 6 month follow-up CRF.

This document and the information contained herein is considered Proprietary and Confidential and may not be reproduced, used or disclosed without written permission from Edwards Lifesciences LLC.

#### Anticipated Adverse Events

A variety of device and procedure related complications are expected to occur in subjects undergoing mitral valve replacement These predefined complications are considered adverse events. (See Appendix 8 for definitions of anticipated adverse events).

#### **Unanticipated Adverse Device Effect** (US CFR 21-812.3)

An unanticipated adverse device effect is defined as "Any serious adverse effect on health or safety or any life-threatening problem or death caused by, or associated with, a device, if that effect, problem, or death was not previously identified in nature, severity, or degree of incidence in the investigational plan or application (including a supplementary plan or application), or any other unanticipated serious problem associated with a device that relates to the rights, safety, or welfare of subjects.

NOTE: By definition a UADE is considered Serious, therefore for the purposes of reporting at European sites under ISO 14155, all UADEs should be reported as Serious Adverse Device Effects (SADEs).

This study will also report adverse events from non-US sites under the following additional classifications:

#### Adverse Device Effect (ADE): (/SO14155-1:2009)

An Adverse Device Effect is defined per ISO 14155 as "Any untoward and unintended response to a medical device", including events that result from insufficiencies or inadequacies in the Instructions for Use, the deployment of the device, as a result of user error. Both the study subject or user may experience an adverse device effect if the event is due to user error. (Meddev 2.12)

This document and the information contained herein is considered Proprietary and Confidential and may not be reproduced, used or disclosed without written permission from Edwards Lifesciences LLC.
#### Serious Adverse Event (SAE): (ISO 14155-1:2009)

An serious adverse event is defined as an event that:

- a) led to death
- b) led to a serious deterioration in the health of a subject that
  - 1) resulted in a life-threatening illness or injury,
  - resulted in a permanent impairment of a body structure or a body function,
  - required in-patient hospitalization or prolongation of existing hospitalization, or
  - 4) resulted in-patient medical or surgical intervention to prevent permanent impairment to body structure or a body function
- c) led to fetal distress, fetal death or a congenital abnormality or birth defect.

#### Serious Adverse Device Effect (SADE): (ISO 14155-1:2009)

As Serious Adverse Device Effect is defined as an "adverse device effect that has resulted in any of the consequences characteristic of a Serious Adverse Event or that might have led to any of these consequences if suitable action had not been taken or intervention had not been made or if circumstances had been less opportune".

## 7.1 Adverse Event Reports

All adverse events regardless of device relationship shall be recorded and reported to Edwards Lifesciences.

Adverse events related to the study device, unanticipated adverse device effects (UADEs) and serious adverse events (SAEs) or adverse device effects (SADEs) must be reported to Edwards within 2 business days of knowledge of the event.

This document and the information contained herein is considered Proprietary and Confidential and may not be reproduced, used or disclosed without written permission from Edwards Lifesciences LLC.

Following initial notification, the Investigator shall submit a written summary of the event (including the time and date of onset, complete description of the event, severity, duration, actions taken and outcome) to the Heart Valve Therapy Clinical Research department either via email to [contact], or by fax to [contact] and to the reviewing IRB or Ethics Committee.

Edwards shall report the event to the appropriate regulatory authorities per country specific regulations and respective adverse event classifications.

## 7.2 Medical Device Reporting (MDR)

Edwards will be responsible for reporting events to the Food and Drug Administration in accordance with 21 CFR 803 Medical Device Reporting. Examples of MDR events include the Safety Endpoints listed in section 3.3 above.

## 7.3 Medical Device Reporting Outside the United States

Edwards will be responsible for reporting events to the Country Competent Authorities and EU Notified Bodies in accordance with MedDev 2.7.1 Dec 2009. Guidelines on Medical Devices.

## 8.0 RISK ANALYSIS

The purpose of this study is to confirm reasonable safety and effectiveness for the use of the Magna Mitral valve when compared to the Objective Performance Criteria from Annex R, Table R.1 per ISO 5840 as proposed by the US FDA in the Heart Valve Guidance draft 2009.

This document and the information contained herein is considered Proprietary and Confidential and may not be reproduced, used or disclosed without written permission from Edwards Lifesciences LLC.

## 8.1 Potential Risks

Risks known to be associated with the use of bioprothestic heart valves and valve replacement procedures may include, but are not limited to the following: angina, cardiac arrhythmia, endocarditis, heart failure, hemolysis, hemolytic anemia, hemorrhage (bleeding), local and/or systemic infection, myocardial infarction, prothetic leaflet entrapment, prosthetic nonstructural dysfunction, prosthetic pannus, prosthesis perivalvular leak, prosthetic regurgitation, prosthetic structural deterioration, prosthesis thrombosis, thromboembolism, multi-system organ failure, non-cerebral blood clot, pericardial effusion or cardiac tamponade, respiratory failure, stroke or transient ischemic attack

Additional risks associated with the use of Carpentier-Edwards PERIMOUNT mitral valve models have been compiled from critical literature reviews and from reports received through the Edwards Lifesciences complaint handling system. These risks may include but are not limited to the following: stenosis, regurgitation through an incompetent valve, ventricular perforation by stent posts, malfunctions of the valve due to distortion at implant, and fracture of the wireform frame.

As a result of these complications, a study subject may require:

- reoperation or
- explant and replacement of the Edwards Magna Mitral valve,

OR may experience:

- permanent disability
- death

This document and the information contained herein is considered Proprietary and Confidential and may not be reproduced, used or disclosed without written permission from Edwards Lifesciences LLC.

Although the Magna Mitral valve models have undergone extensive bench top and animal testing in accordance with the FDA guidance document, not all models required clinical trial data due to minor modifications.

## 8.2 Minimization of Risks

Potential study subjects will undergo thorough preoperative assessments and only subjects who meet the study eligibility criteria will be allowed to participate in the study. Subjects will be closely followed intraoperatively and carefully monitored in the early post-operative period through hospital discharge. Study subjects will undergo regular clinical examinations including serial blood studies to assess for hemolysis and anemia, and Doppler echocardiography examinations to assess hemodyamic performance of the valve throughout the duration of the study.

The study devices were developed, designed and manufactured under an ISO compliant quality system and in accordance with applicable guidelines and international standards including the ISO14971 Medical Design Risk Management process. The biocompatibility of all components of the valve has been established in compliance with international standards (ISO10993-1), and designed to provide hemodynamic performance similar to other commercially available valves. The sewing ring has been designed to facilitate sewing to and seating in the mitral annulus and valve materials have been selected for their durability and resistance to wear and fatigue.

The study device should be used with caution in the presence of severe systemic hypertension or when the anticipated subject longevity is longer than the known longevity of the prosthesis. Subjects undergoing dental procedures should receive prophylactic antibiotic therapy to minimize the possibility of prosthetic infection.

#### 8.2.1 Physician Training

This document and the information contained herein is considered Proprietary and Confidential and may not be reproduced, used or disclosed without written permission from Edwards Lifesciences LLC.

Each investigator will have received appropriate product training in the study protocol and investigational plan requirements by the sponsor or sponsor representative.

Data from all study sites will be monitored as it is submitted to Edwards. Qualified employees of Edwards, or a designated contract research organization (CRO), under contract with Edwards will conduct monitoring visits at the initiation of the study, periodically during the course of the study and upon study completion to assess ongoing compliance with the study protocol and adherence to protocol requirements.

#### 8.2.2 Clinical Events Review Committee

A Clinical Events Committee (CEC) will be responsible for the ongoing review of all reported adverse events and will serve to adjudicate the relationship of the event and the study device or surgical procedure. The CEC will be composed of independent physicians familiar with the treatment of valvular heart disease and cardiac surgery and a statistician will evaluate the rates of complications, including deaths and explants for all subjects in the study as well as the hemodynamic performance of the Magna Mitral valve. The CEC will be tasked with identifying any issues such as higher than expected complication and/or death rates or unanticipated adverse events or hemodynamic performance that is substantially better or worse than expected, to determine if the study should be stopped or changed at any time.

## 8.2.3 Echocardiography Core Laboratory

An Echo Core Lab will provide unbiased independent review of valve hemodynamics and potential valve complications over time.

This document and the information contained herein is considered Proprietary and Confidential and may not be reproduced, used or disclosed without written permission from Edwards Lifesciences LLC.

#### 8.2.4 Data Quality Assurance

Edwards has designed quality assurance procedures to ensure that complete, accurate and timely data are collected, all Study Protocol requirements are followed and that all complications and adverse events are reported in a timely manner.

Standardized case report forms (CRFs) will be used for the collection and recording of data at all study sites. Investigators are responsible for the timely completion and submission of these forms to the Clinical Monitor.

Incoming data are reviewed to identify inconsistent or missing data and adverse events. Data problems will be addressed by telephone or written communication with the study sites and/or during site visits. All hard copy forms and data files will be secured to ensure confidentiality.

Pre-operative diagnostic tests will be evaluated by the Investigator and other appropriate professionals at the study sites to determine the study subject's suitability for the clinical study.

Investigators shall maintain all source documents required by regulation, including diagnostic test reports, laboratory results, completed case report forms, supporting medical records and informed consents. The source documents will be referenced during regular monitoring visits to verify the information documented on the case report forms.

## 8.3 Potential Benefits

In general, young patients, patients with chronic atrial fibrillation and who require longterm anticoagulation and patients who wish to minimize the chance of re-operation

This document and the information contained herein is considered Proprietary and Confidential and may not be reproduced, used or disclosed without written permission from Edwards Lifesciences LLC.

should chose a mechanical valve. Patients with implanted mechanical valves are generally considered to have a serious threat of thromboembolic adverse events thus requiring a lifelong anti-thromboembolic therapy. Even with adequate anti-thromboembolic therapy, the risk of adverse events is significant, particularly when the risk of serious hemorrhage is considered.

For patients in whom anticoagulation therapy is contraindicated and for patients who are in sinus rhythm and who wish to avoid anticoagulation therapy, a bioprosthetic (tissue) valve is preferred. The ACC/AHA Guidelines for Management of Patients with Valvular Heart Disease states that it is reasonable to implant a mitral bioprostheses in patients age 65 years and older with long standing atrial fibrillation. A mitral valve replacement may be also considered appropriate for patients less than 65 years of age who are in sinus rhythm with lifestyle considerations who have been informed of the risks of reoperation vs. anticoagulation.

Bioprosthetic valves have the advantage of low thrombogenicity, which must be weighed against limited long term durability and subsequent hemodynamic deterioration and the risk of reoperation. Hemodynamically, the bovine pericardial valves maximize use of the flow area and minimize flow resistance, thus providing a better solution to flow problems than the porcine valves. The bovine pericardium has superior intrinsic properties to porcine aortic valve, notably in terms of collagen content and tolerance to high bending curvatures which can favorably influence the long-term mechanical durability of pericardial valves.

Although the proven longevity of bioprostheses is not as long as that of some of the currently available mechanical valves, results from a multi-center study involving the original Carpentier-Edwards PERIMOUNT mitral valve model 6900 showed actuarial freedom from explant due to structural valve deterioration (SVD) to be  $68.8\% \pm 4.7\%$ . Results from the same study showed overall actuarial survival rate to be  $37.1\% \pm 3.3\%$  and valve related survival rate to be  $63.1\% \pm 4.4\%$  at 14 years. Actuarial freedom from

This document and the information contained herein is considered Proprietary and Confidential and may not be reproduced, used or disclosed without written permission from Edwards Lifesciences LLC.

adverse events at 14 years was as follows: thromboembolism,  $83.8\% \pm 3.2\%$  and hemorrhage,  $86.6\% \pm 3.2\%^{20}$ . Subjects participating in this study will be closely followed to monitor their health and safety.

#### 8.4 Risk /Benefit Analysis

The Clinical Risk Assessment has been revise to consider the Model 7300/7300TFX. Please refer to Appendix 9 attached.

This document and the information contained herein is considered Proprietary and Confidential and may not be reproduced, used or disclosed without written permission from Edwards Lifesciences LLC.

## 9.0 STATISTICAL ANALYSIS

Please refer to Sections 11.1 - 11.3 for study sample size calculations, and a summary of the study analysis plan . Sections 11.4 and 11.5 address the issues of data poolability and missing data. Unless otherwise noted, all statistical tests will be performed at the  $\alpha$  = 0.05 level.

## 9.1 Sample Size Calculation

The sample size calculation for the trial is based on the primary safety endpoints. The linearized rates for thromboembolism, all hemorrhage, all perivalvular leak, and endocarditis will be compared to the Objective Performance Criteria from Annex R, Table R.1 per ISO 5840 as proposed by the US FDA in the Heart Valve Guidance draft 2009. These OPC are presented in Table 11.

Adverse Event	OPC
Thromboembolism	2.5
All Hemorrhage	1.4
All Perivalvular Leak	1.2
Endocarditis	1.2

Table 11: Safety OPC

More specifically, a statistical test based on the Poisson distribution will be performed for each of these adverse event rates to evaluate whether it is less than 2 times the appropriate OPC. Thus, the null and alternative hypotheses for each adverse event are as follows:

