## $H_0: \lambda \geq 2 \cdot OPC$

## $H_A: \lambda < 2 \cdot OPC$

This document and the information contained herein is considered Proprietary and Confidential and may not be reproduced, used or disclosed without written permission from Edwards Lifesciences LLC.

where  $\lambda$  is the linearized rate for the given adverse event (thromboembolism, valve thrombosis, all hemorrhage, all perivalvular leak, and endocarditis) computed when the total subject years reaches 808 and *OPC* denotes the relevant OPC. The test statistic for each adverse event is of the form:

$$Z = (\lambda - 2 \cdot OPC) / \sqrt{\lambda} .$$

 $H_0$  is rejected in favor of  $H_A$  if Z is less than -1.645, the lower 5% percentile of the standard normal distribution. Grunkemeier, et al. have demonstrated that 800 subject life-years is adequate to test against the smallest OPC of 1.2% per subject year (excluding valve thrombosis, and stratification for major versus minor hemorrhage, and perivalvular leak) with Type I and Type II error controlled at the .05 and .20 levels, respectively.

The proposed subject enrollment is calculated to ensure that at least 101 subjects survive to 8 years post implant. These 8\*101 = 808 life years in addition to the life years from those subjects not surviving to 8 years will more than fulfill the 800 life-years required by Grunkemeier, et al..

Sample size calculation for primary effectiveness endpoint is based on a test of the hypothesis:

 $H_0: p \le 75\%$  $H_A: p > 75\%$ 

where *p* is the proportion of the subjects in NYHA Class I or Class II at 8 years post implant. The expected proportion of the alive subjects in NYHA class I or II at eight years is approximately 90%, based on 7 year follow up data for the Carpentier-Edwards PERIMOUNT 6900/6900P valve (this proportion is essentially constant across each annual visit). Based on this expected proportion, a sample size of 45 subjects provides 85% power to test the hypothesis that the true proportion is greater than 75% using an exact binomial test. Thus, the sample size of 101 subjects with NYHA data at 8 year post implant is more than adequate to provide sufficient power.

This document and the information contained herein is considered Proprietary and Confidential and may not be reproduced, used or disclosed without written permission from Edwards Lifesciences LLC.

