#### **Repeated events**

Some valve-related events, such as thromboembolism and bleeding, can occur repeatedly. Although estimating freedom from any such event is meaningful, even more important is enumerating all such events. Some of the previously mentioned methods have been devised or extended to consider repeated events in the same patient. A simple and widely used approach uses linearized rates, as described previously, to estimate the incidence of multiple events. These rates should be considered only approximate unless the risk of recurrent events is the same as for initial events (which is often not the case). If it is not, a simple approach is to restart time zero at each event occurrence.

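### For thromboembolism and hemorrhage, the 5% error of the Poisson test against 2 x OPC holds only if repeat events within a subject are independent, and the plan has no check on this

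*Combined protocol and SAP*

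**What the plan says.** Section 9.1 sets four primary safety tests, one each for thromboembolism, all hemorrhage, all perivalvular leak and endocarditis: "a statistical test based on the Poisson distribution will be performed for each of these adverse event rates". Each test asks if the true rate lies below double its OPC. The null is rejected "if Z is less than -1.645, the lower 5% percentile of the standard normal distribution". An exposure of 800 subject-years is called adequate for the "smallest OPC of 1.2% per subject year"; the plan describes that test as one "with Type I and Type II error controlled at the .05 and .20 levels, respectively". The rate is to be computed when total exposure reaches 808 subject-years. The OPCs in Table 11 are 2.5 for thromboembolism and 1.4 for all hemorrhage (% per year), so the limits under test are 5.0 and 2.8.

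Section 9.3.1 defines the late linearized rate as events per subject-year. Counting only the first event is specified for explant and reoperation (Section 9.4.2) and not for the primary endpoints. Sections 9.1 to 9.7 contain no over-dispersion term, robust variance or repeat-event rule for the OPC test.

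The guideline reproduced in Appendix 1 is adopted for clinical assessment of adverse events in Section 6.1.2. Under its heading on repeated events it says: "Some valve-related events, such as thromboembolism and bleeding, can occur repeatedly". On linearized rates that include repeats it adds: "These rates should be considered only approximate unless the risk of recurrent events is the same as for initial events", and notes that this condition often fails.

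**The concern.** A Poisson test takes the variance of the event total to equal its mean. That is true if events arise independently. If some subjects carry a higher rate than others, or one event raises the chance of the next, the total varies more than the test allows, and its lower tail falls below the cut-off more often than stated.

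The error would run in the unfavorable direction: a valve whose true rate sits at twice the OPC would pass more than 5% of the time. The plan itself expects subjects to differ in risk, since Section 9.3.1 stratifies thromboembolism by atrial fibrillation, sinus rhythm and pacemaker. The guideline names thromboembolism and bleeding as the recurring events, so the point is confined to those two tests.

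**Working it through.** **1. The plan's own figure.** Take H0 as 2.4% per year and the true rate as 1.2% per year (true rate equal to the OPC is an assumption). The smallest exposure at which an exact one-sided Poisson test has size at most .05 and power at least .80 is 811 subject-years (reject at 12 or fewer events; size .0495, power .816). That is within 3% of 800, so the stated figure reproduces, under independent events.

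**2. Cut-offs at 808 subject-years.**
- Thromboembolism: expected events at the limit 0.05 x 808 = 40.4; reject at 29 or fewer; size .038.
- Hemorrhage: 0.028 x 808 = 22.6; reject at 14 or fewer; size .037.

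Because counts are discrete, both exact tests start with some slack. Writing the variance as φ x mean (negative-binomial total), the size passes .05 only when φ exceeds about 1.17 (thromboembolism) or 1.19 (hemorrhage).

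**3. From between-subject variation to φ.** Let subject i have exposure t_i and rate λ·g_i, with g_i gamma, mean 1, variance v. Then

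φ = 1 + λ·v·(Σt²/Σt).

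Assumed exposure pattern: 250 subjects (Section 9.1), of whom 56% x 250 = 140 are followed for 8 years and 110 are spread evenly over 0 to 8 years.
- Σt ≈ 140 x 8 + 110 x 4 = 1,560
- Σt² ≈ 140 x 64 + 110 x 64/3 ≈ 11,307
- Σt²/Σt ≈ 7.25; scaled to 808 subject-years, 7.25 x 808/1,560 ≈ 3.75

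So φ ≈ 1 + 0.05 x 3.75 x v for thromboembolism and 1 + 0.028 x 3.75 x v for hemorrhage. The error columns come from simulating this model.

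| v (assumed) | φ, thromboembolism | error | φ, hemorrhage | error |
|---|---|---|---|---|
| 1 | 1.19 | 5.3% | 1.11 | 4.4% |
| 2 | 1.38 | 6.5% | 1.21 | 5.2% |
| 4 | 1.75 | 8.9% | 1.42 | 6.6% |

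**4. Longer exposure.** Section 9.1 says that the 808 years come from the 101 completers alone and that other subjects add to them. If all of an assumed total of about 1,557 subject-years were analyzed, each subject would contribute more time and so more repeats. Over the same range of v, the error would be about 7.8% to 14.8% for thromboembolism (cut-off 63) and 5.7% to 9.7% for hemorrhage (cut-off 32).

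**5. A second model.** Suppose a share q of first events is followed by exactly one repeat, so φ = (1 + 3q)/(1 + q). At 808 subject-years, q of 10%, 20% and 30% gives errors of .051, .063 and .072 for thromboembolism and .050, .061 and .071 for hemorrhage.

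**6. Evidence on clustering.** The Instructions for Use in Appendix 4 tabulate event counts and Kaplan-Meier freedom for models 6900 and 6900P. Under independent events at a constant late rate, 5-year freedom would be (1 − early events/N) x exp(−late rate x (5 − 30/365.25)). For 6900P thromboembolism: (1 − 4/209) x exp(−12/856.24 x 4.918) = 91.6%.

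| | Poisson-implied | Kaplan-Meier [95% CI] |
|---|---|---|
| 6900 thromboembolism | 95.1% | 96.1% [93.8, 98.5] |
| 6900 anticoagulant-related hemorrhage | 95.4% | 97.1% [95.2, 99.0] |
| 6900P thromboembolism | 91.6% | 91.3% [85.8, 94.7] |
| 6900P bleeding | 90.6% | 91.9% [86.5, 95.2] |

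Clustering would push the Kaplan-Meier value above the Poisson-implied one. Three of the four lie that way, by 1.0 to 1.7 points, but every Poisson-implied value is inside the interval. The check is rough, because the hazard need not be constant.

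**The case against.** The strongest reply is that the adopted guideline allows what the plan does. Appendix 1 describes linearized rates as a common, simple approach to multiple events and accepts Poisson-based confidence intervals for them. Its caveat about recurrence gives no direction, and its suggested remedy is to restart the clock at each event, not a robust variance. This stands: the method is permitted, and the point concerns only the claim that error is controlled at .05.

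Second, some clustering is already removed. Under its definition of embolism, the guideline counts a short burst of transient events once. Under endocarditis, emboli, bleeds and leaks that accompany active infection are counted only there. Stratification by rhythm and Kaplan-Meier freedom from each event are also planned. These reduce the problem, but they leave lasting differences between subjects and repeat bleeds, and neither planned analysis is tested against the OPC.

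Third, the form of the test matters more than clustering. The Z printed in Section 9.1 has no exposure term. Read on the event-count scale, its size at 808 subject-years is already .076 (thromboembolism) and .094 (hemorrhage) without clustering. Read literally with rates in % per year, it would reject at 19 or fewer thromboembolic events, with size about .0001. That is a separate matter. The figures here assume an exact Poisson cut-off.

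A reader might infer that the counts are over-dispersed and the primary safety tests therefore too lenient. The documents do not support that: they give no dispersion figure, and the predecessor tables do not show strong clustering. Nor do they support extending the point to perivalvular leak or endocarditis.

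**Conclusion.** The point holds as a conditional one, for thromboembolism and all hemorrhage only. The stated 5% error requires independence of repeat events, which the plan neither states nor checks and which its own reporting guideline says often cannot be assumed.

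At the planned exposure the likely inflation is modest. Across the assumed range it is a few percentage points at most for thromboembolism. For hemorrhage the error stays below 5% at the low end and reaches 6.6% only at the extreme. It becomes material (up to about 15%) only if heterogeneity is large and all accrued follow-up is analyzed.

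These sizes rest on an assumed gamma variance, an assumed follow-up pattern and an exact Poisson cut-off; none of the three is fixed by the documents. The point is minor, and confidence in any particular size is low.

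**What to change.** Keep the linearized rate as the estimate and the Poisson test as the primary test. Add to Section 9.3.1, for thromboembolism and all hemorrhage:

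- A statement of how repeat events in a subject are counted, including whether the burst and endocarditis rules of Appendix 1 apply to the primary counts.
- A pre-specified one-sided 95% upper bound from a Poisson model with subject-level sandwich variance on the log-rate scale: r x exp(1.645 x SE), where SE = √Σ(y_i − r·t_i)² / Σy_i, y_i is the subject's event count, t_i the subject's exposure and r the overall rate. Report it beside the Poisson bound as a sensitivity analysis.
- A sentence that any claim of meeting 2 x OPC will be qualified if the robust bound does not lie below the limit.

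The scale must be named. On the log scale, requiring both the Poisson test and the robust bound to pass would bring the simulated error at 808 subject-years to 4.8%, 5.1% and 5.7% for thromboembolism and 4.1%, 4.5% and 5.0% for hemorrhage (v = 1, 2, 4). A linear-scale bound changes almost nothing.

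The cost is a little programming, no new data and a slightly wider bound. As a sensitivity analysis it does not alter the power of the primary test. If the sponsor chose to require both bounds, power at the OPC would fall by under 1 point without clustering and by about 4 to 6 points at the extreme of the assumed range.
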